*Daily Contact Testing LFD tests will initially be performed as an assisted test in the school setting. Results will be recorded electronically and reported to NHS Test and Trace. On non-school days participants will not receive LFD testing. Where day 7 of DCT falls on a Saturday or Sunday, a negative LFD test will be needed to exit DCT testing. Once a reliable protocol for home testing and recording of LFD is available, and relevant regulatory approvals are in place, participants may be offered the option for at-home self-test DCT.

Additionally research component: Consenting first-order contacts will be tested via self-administered qRT-PCR at days 2 and 7 from the point of being notified they are a

⁵ Biweekly LFD active case finding among staff is already underway outside the context of this evaluation

⁶ For clarity, the day on which they are notified they are a contact is Day 0

close contact⁶. These qRT-PCR samples will be collected for research purposes and run in batches every two weeks, after which results will be available for participants.

2. Control Arm

- Public Health Intervention: First order contacts of a COVID-positive index case will be instructed to self-isolate according to national guidelines (i.e. there will be no change to the public health intervention compared to non-participation in the evaluation). The contacts of all first-order contacts (i.e. 'second-order contacts') will be identified to allow the determination of secondary attack rate.
- b. Additionally research component: Consenting contacts will be provided with two home qRT-PCR test kit and asked to self-test at days 2 and 7 from the point of being notified they are a close contact⁶. These qRT-PCR samples will be collected for research purposes and run in batches every two weeks, after which results will be available for participants.

Figure 2: Schematic of study design and participation sub-groups

Consideration was given to a stepped-wedge study design where schools would introduce daily contact testing in waves. This was not pursued as part of this protocol due to the operational feasibility of this design.

Consideration for comparator testing regimes and groups of varying prevalence as part of the evaluation were considered but will not be part of this phase.

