3.4 Lateral Flow Device Testing

LFD antigen testing will be via two delivery models:

- 1. Supervised anterior nares swabbing, and device use within a school's 'Asymptomatic Testing Site (ATS)' model. The workforce for this will be trained according to national NHS T&T standard process.
- 2. Home or Self-testing will be made available once reliable operational delivery models are developed, and subject to the relevant regulatory approvals being received.

3.5 qRT-PCR Testing

The purpose of the qRT-PCR test component is to determine the number of first-order contacts which are positive with PCR but negative with LFD during DCT. This will determine the false negative rate of DCT. First-order contacts will be prioritised in the daily testing schedule in the school to ensure they are tested at the beginning of the day.

The swabbing method for qRT-PCR swabbing will be throat-and-nose as per standard NHS T&T practice. If throat-and-nose swabbing is not tolerated, anterior nares swabbing may be used. Schools / participants should record which swabbing method is used each day. Participants should self-swab under supervision in alignment with national NHS T&T guidance.

qRT-PCR swab samples will be transported to PHE Porton Down, stored at -20°C and processed in batches every two weeks. Results will be available to participants after this time. This process is being implemented to prevent participants (in either stud arm) from receiving information on their COVID-19 status that they will not receive as part of the real-world public health intervention. This will be communicated to potential participants via the Participant Information Leaflet and ICF prior to enrolment in the study.

qRT-PCR testing will not form part of scaled LFD-enabled testing of asymptomatic close contact groups in schools. As such, the evaluation framework for the study will not consider the acceptability, tolerability or operational performance of the qRT-PCR testing component.

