3.6 Assessment of End-Points

Please see the glossary at the start of this protocol for definitions

Co-Primary End-Points

(i) Number of school days missed among those eligible to be in school.

Daily school attendances will be obtained from the school register and absences recorded with reconciliation with COVID-19 associated absences. This will be compared between study arms, to historic schools' data, and to national schools' benchmark data collected via a survey of non-participating schools.

(ii) Estimated number of in-school COVID-19 transmission events

The number of positive cases will be obtained from the following sources:

- 1. Weekly LFD active case finding (Control and Intervention Arms)
- 2. Symptomatic individuals' NHS Test and Trace results obtained from Community Testing routine data (Control and Intervention Arms)
- 3. In-school LFD DCT testing (Interventional Arm).

Positivity rates will be reported for each source separately to facilitate like-for-like comparison between arms

Epidemiological links between cases will be obtained from the NHS Test & Trace Contact Tracing and Advice Service data base. Additional links will be obtained by membership of school-reported contact groups. Onward transmission from the index case will be determined by the following:

• Genomic sequence of virus: The additional PCR swab collected from positive individuals will be used to determine the whole genomic sequence of isolates. A sample of apparent links will be assessed with comparisons of whole genome sequencing. The diversity of genetic sequences both in the schools and the

community (routinely determined by COG) will be used to help interpret the results. Preliminary work currently undertaken will determine the appropriate genetic distance to be used to exclude a direct transmission event between individuals. This is likely to be 2 SNPs.

- Plausible epidemiological link (e.g. membership of same close contact group)
- For positive individuals identified in DCT the DMIC will review all available data to determine if the individual's infection was likely to have resulted from onward transmission from the index case, or via co-infection from an unknown 'upstream' positive or out-of-school positive case.

Secondary End-Points

(iii) Number of positive first-order contacts missed by daily LFD testing (Intervention arm only).

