Routine qPCR of first-order contacts will be used to determine the performance of DCT testing with LFDs. Comparisons of PCR with the same day LFD will allow comparison between CT values and LFD results in a 'real world setting' These comparisons can also be used to compare the relative performance between assisted school-based testing and home/self-testing.

(iv) Number of COVID-19 cases transmitted to the first-order contacts of index cases ("primary attack rate").

The first-order close contacts of all index cases will be identified by the school based on their existing close contact management policy. LFD DCT testing and (for symptomatic individuals) routine NHS Test and Trace PCR testing will be used to calculate primary attack rate.

As above, genomic sequencing will be used, wherever possible, to exclude non-direct transmission events.

(v) Number of COVID-19 cases transmitted to the second-order contacts of index cases ("secondary attack rate").

The second-order contacts of all index cases will be identified (regardless of the COVID-19 status of the DCT-contacts) as described in Section 3.7. The COVID-19 status of these second-order contacts will be measured in two ways:

- i. Where the second-order contact is a consented participant in this study their COVID-19 status will be assessed by weekly LFD active case finding, and records kept by the school of any participants who become symptomatic and test positive via standard NHS Test and Trace community testing.
- ii. Where the second-order contact is not a consented participant in this study (e.g., household contact of first-order contact), analysis of routine NHS Test and Trace data will be used to determine if they subsequently become symptomatic and test positive in the community setting.

As above, genomic sequencing will be used, wherever possible, to exclude non-direct transmission events.

(vi) Number and proportion of school attendees testing COVID-19 positive in weekly active case finding.

LFD results and school attendance registers will be used to calculate active case finding rate. This will be compared between study arms, and to national schools' benchmark data collected via a survey of non-participating schools.

(vii) Proportion of student and staff who accept an offer of weekly active case finding testing with LFD devices.

Schools will maintain consenting records to allow participation rates to be calculated.

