3.7 Identification of Second-Order Contacts

As discussed above, the rate of COVID-19 positivity in the second-order contacts of index cases (i.e. the contacts of first-order contacts) will be an endpoint used to assess the public health effectiveness of DCT for school populations. Several methods will be used to identify the second-order contacts of index cases:

• In-school secondary contacts: As part of their existing COVID-19 management policy schools are required to segment their population into distinct 'bubbles' (e.g., year group), membership of which is unique. Members of one bubble should not be interacting with members of another. As a result, all the contacts of a member of a specific bubble should also be members of the same bubble.

In the event of a positive index case within a bubble, the school will identify those bubble members it considers to be close contacts of the index case (this will often not be the entire bubble). These close contacts (i.e. 'first-order contacts' in the context of this study) are subject to self-isolation or DCT depending on their arm.

All other members of the index case's bubble will be considered second-order contacts for the purposes of this study. Membership of each bubble will be provided by participating schools at the start of the study, and should not vary during the study.

• Household contacts of first-order contacts: Another group of second-order contacts are individuals who live in the same household as a first-order contact. These may attend the same school or may not. These individuals will be 'identified' by querying routinely collected NHS Test and Trace testing data for individuals with the same residential address as any first-order contact. The method to identify household contacts will only identify household contacts who are in Test and Trace systems.

Within the scope of this study we do not intend (for operational reasons) to identify non-school, nonhousehold contacts of first-order contacts. As first-order contacts are required to maintain selfisolation outside the school environment (even if they are undertaking DCT) this group should be minimal in size. However, it is an acknowledged limitation of the study. We also do not intend (for similar reasons) to identify individuals within the school who are not a member of the same bubble as a first-order contact but have had close contact with them. We acknowledge this as another limitation of the study.

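### The primary attack rate (end-point iv) is built on sources that detect first-order contacts' infections unequally in the two arms, which biases the comparison against daily contact testing

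*Protocol*

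**What the plan says.** Section 3.6 (iv) names the data sources for the primary attack rate: "LFD DCT testing and (for symptomatic individuals) routine NHS Test and Trace PCR testing will be used to calculate primary attack rate". The definitions table gives that rate as the share of an index case's first-order contacts who are later diagnosed.

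The daily LFD source belongs to one arm. Under co-primary (ii), section 3.6 lists it as "In-school LFD DCT testing (Interventional Arm"). For the control arm, section 3.1 says: "First order contacts of a COVID-positive index case will be instructed to self-isolate according to national guidelines". End-point (iii) is expressly limited to the intervention arm; (iv) carries no such limit.

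Research PCR is planned in both arms on the same days. For the intervention arm, section 3.1 has "Consenting first-order contacts will be tested via self-administered qRT-PCR at days 2 and 7"; for control, "Consenting contacts will be provided with two home qRT-PCR test kit and asked to self-test at days 2 and 7". Section 3.5 gives its use: "The purpose of the qRT-PCR test component is to determine the number of first-order contacts which are positive with PCR but negative with LFD". Section 3.6 (iii) agrees: "Routine qPCR of first-order contacts will be used to determine the performance of DCT testing with LFDs". The statistical paragraphs at the end of section 5.3 use PCR to judge DCT performance and to stratify secondary transmission by the DCT contact's results. They do not bring it into the primary attack rate.

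**The concern.** A rate compared between arms needs the same chance of detection in each. Here an intervention contact who accepts DCT can be found by daily LFD or after symptoms, whereas a control contact can be found only after symptoms. A higher attack rate under DCT would then appear even if transmission were identical.

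This matters because the second study hypothesis is that transmission under DCT is no higher than in control, and section 3.9 sets no margin for it. An independent committee is to judge the transmission results. An attack rate raised by more intensive testing could colour that judgement.

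The PCR that could give a common measure has no stated use in control. Its declared purpose, counting infections that daily LFD misses, cannot apply to contacts who have no daily LFD.

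**Working it through.** **1. Which sources can detect a contact's infection under (iv)**

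| Contact | DCT LFD | Symptomatic Test and Trace PCR | Day 2/7 PCR |
|---|---|---|---|
| Intervention, accepts DCT | yes | yes | collected, not assigned to (iv) |
| Intervention, declines DCT | no | yes | unclear whether collected (see objection) |
| Control | no | yes | collected if consenting, not assigned to (iv) |

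Weekly LFD case finding is listed for co-primary (ii) and for second-order contacts in (v), but not for (iv). It is also initially done in school, where isolating contacts are absent.

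**2. The nearest figures in the plan**

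The protocol gives no expected value for (iv). Section 3.9 expects 70% of contacts to take up DCT (0.70 × 50 = 35) and about 2 of them to be LFD-positive (5% of 35 = 1.75, which agrees). Only the 70% uptake is needed below.

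**3. Size of the bias when the true rates are equal**

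Inputs:
- p = true attack rate, the same in both arms. It cancels from the ratio.
- u = DCT uptake = 0.70 (section 3.9).
- s = share of infections found by symptomatic testing, assumed 0.3 to 0.7.
- L = share of the remaining infections found by daily LFD, assumed 0.5 to 0.8.

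Formulas:
- Control measured rate = p × s
- Intervention measured rate = p × [u × (s + (1 − s) × L) + (1 − u) × s]
- Ratio = 1 + u × (1 − s) × L / s

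| s | L = 0.5 | L = 0.65 | L = 0.8 |
|---|---|---|---|
| 0.3 | 1.82 | 2.06 | 2.31 |
| 0.5 | 1.35 | 1.455 | 1.56 |
| 0.7 | 1.15 | 1.195 | 1.24 |

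Lowest: 1 + 0.70 × 0.3 × 0.5 / 0.7 = 1.15. Highest: 1 + 0.70 × 0.7 × 0.8 / 0.3 = 2.31. At the midpoint, with an illustrative p of 5%, control reads 0.05 × 0.5 = 2.50% and intervention reads 0.05 × [0.70 × (0.5 + 0.5 × 0.65) + 0.30 × 0.5] = 3.64%, with no real difference.

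**4. The same check with day 2/7 PCR in both arms**

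Take equal PCR sensitivity and let the returned fraction be r in each arm.
- Denominator of PCR-tested contacts: r cancels within each arm, and the expected ratio is 1.00.
- Denominator of all contacts: the ratio is r(intervention) / r(control). Assumed returns of 80% and 60% give 1.33; 70% and 40% give 1.75.

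The choice of denominator therefore matters as much as the choice of source. The 1.00 also assumes that contacts who return swabs are comparable between arms.

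**The case against.** **It is a secondary end-point.** Power rests on attendance, and the committee's judgement in section 3.9 concerns transmission events, which are co-primary (ii). No sample size or alpha depends on (iv). This stands and limits the severity.

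**Reporting by source.** Section 3.6 undertakes to report positivity separately by source, so the authors knew that the sources differ. That sentence sits under (ii), and the DCT LFD source has no control counterpart to set beside it. A comparison on symptomatic cases alone would be possible in both arms, but (iv) does not define one.

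**Leave it to the SAP.** A SAP not shown here may add PCR. But the protocol is not silent: it names the sources, and a SAP that followed it would inherit the imbalance.

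**PCR is not free of bias either.** This stands. Sections 4.2.1 and 4.2.3 say that a missed swab is no protocol violation. The opening of section 4 attaches the swabs to those taking part in DCT and does not describe the others further, while section 3.1 refers to consenting first-order contacts. Decliners may therefore be missing from the intervention arm's PCR. A reader might infer that the plan already holds an unbiased measurement; the documents do not support that.

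**Larger ratios.** If daily LFD found every infection (L = 1), the formula would give 1 + 0.70 × 0.7 / 0.3 = 2.63 at s = 0.3. A reader might take that as the expected distortion. The protocol does not support perfect detection: it collects PCR to count LFD misses, and section 3.1 plans no LFD on non-school days.

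**Household second-order contacts.** Section 3.7 says "The method to identify household contacts will only identify household contacts who are in Test and Trace systems", and a reader might infer a similar between-arm bias in the secondary attack rate. The protocol discloses this limit, applies it to both arms, and gives no ground for assuming different household testing by arm.

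**Conclusion.** The concern holds for end-point (iv). As written, the primary attack rate uses a detection source that only the intervention arm has, so contacts are ascertained unequally and the comparison is biased against DCT. With no true difference, the measured ratio would be about 1.15 to 2.3. This range rests on the protocol's 70% uptake and on assumed detection shares (30-70% by symptomatic testing, 50-80% of the rest by daily LFD) that the documents do not give. The direction does not depend on those values, provided that daily LFD finds some infections that symptomatic testing does not.

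Severity is moderate. The point does not show that the attendance end-point, the power calculation or co-primary (ii) is wrong.

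**What to change.** Amend protocol section 3.6 (iv), and carry the change into the SAP:

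- Calculate the between-arm primary attack rate from the same sources in both arms: the day 2/7 research PCR plus symptomatic Test and Trace PCR.
- Use PCR-tested contacts as the denominator, or state how missing PCR is handled. If the former, define tested by the research swab and take the numerator from the same contacts, so that people tested only because of symptoms do not enter selectively.
- Report PCR return by arm and, within the intervention arm, by DCT uptake.
- Report DCT LFD positives separately, as an intervention-arm result.

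Add to section 3.5 that the PCR component also serves this end-point, so that control-arm PCR has a stated use.

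The cost is a protocol amendment with matching SAP text; the swabs are already planned. The downside is that PCR is voluntary. Incomplete or differential return, including among contacts who decline DCT, would remain a limitation to be reported with the result.

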The number of Covid-19-associated missed days at school is dependent on the number of positive cases identified and the number of contacts of these cases that are self-isolating. Each positive case is self-isolated for 10 days. In the control group all first order contacts will also be self-isolated for 10 days. It is expected that this trial will occur in the summer term when the number of cases in a school will be low. For instance, it is expected that in the control group about 30% of children (and their parents) will consent to participate in regular weekly active case finding testing. For the purposes of the power calculation, it is assumed that the expected number of index cases identified is about 1 outbreak/month. Each index cases will lead to identification of 50 children in their bubble who will need to self-isolate each for 10 days. The number of index cases identified is a Poisson distribution with mean 1/month with each index cases leading to 510 missed school days.

In the intervention group, it is expected that a more complex set of interactions will occur. The ability to avoid self-isolation by DCT is likely to make participation in weekly active case finding testing more

⁸ Quartagrio et al, 'Handling an uncertain control group event risk in non-inferiority trials: non-inferiority frontiers and the power-stabilising transformation' (2020)

attractive with an increase in consent to voluntary weekly active case finding testing to 60%. This in turn will lead to the identification of more positive cases with initially an expected number of 2 different index cases identified per week. However, it is expected that 70% of children will volunteer for DCT and therefore only 15 children (25% of 50) will self-isolate. In addition, about 2 contacts will be identified by LFD testing as positive during DCT (5% of 35). It is expected that these 2 children will only have contacts within the bubble and therefore they will not lead to identification of more children. In all, each index cases will lead to the index cases or 360 missed schools / month

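### The secondary attack rate (endpoint v) pools two follow-up methods chosen by consent, and uptake of weekly testing is expected to differ by arm

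*Protocol*

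**What the plan says.** Endpoint (v) is the secondary attack rate in school-based and household second-order contacts (Protocol 2.1). Section 3.6 (v) fixes two ways of measuring their status.

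- Consented: "Where the second-order contact is a consented participant in this study their COVID-19 status will be assessed by weekly LFD active case finding", plus "records kept by the school of any participants who become symptomatic and test positive via standard NHS Test and Trace community testing".
- Not consented: "analysis of routine NHS Test and Trace data will be used to determine if they subsequently become symptomatic and test positive in the community setting". The protocol's example of this group is a household contact of a first-order contact.

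Section 3.7 sets the in-school denominator without any consent condition: "All other members of the index case's bubble will be considered second-order contacts for the purposes of this study". For household contacts it concedes that the method "will only identify household contacts who are in Test and Trace systems".

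Section 3.9 states the expected uptake. It assumes that "in the control group about 30% of children (and their parents) will consent to participate in regular weekly active case finding testing". In the intervention arm it anticipates "an increase in consent to voluntary weekly active case finding testing to 60" per cent, because DCT offers a way to avoid isolation. Table 1 gives 30% against 40-60%.

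Under co-primary (ii), section 3.6 says that positivity will be reported source by source so that the arms are compared like for like. No such statement is made for (v). Section 5.3 stratifies secondary transmission by the test results of the first-order contact, not by how the second-order contact was followed.

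**The concern.** An asymptomatic infection in a second-order contact can be found if that person is swabbed weekly. It cannot be found if that person is seen only through routine symptomatic data. Both kinds of contact enter one rate. The share followed by the more sensitive route is expected to be larger in the DCT arm, and the intervention itself is the stated reason.

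The detected rate would then differ between arms even if the same proportion of second-order contacts were infected. Section 3.7 says this rate is used to judge the public health effectiveness of DCT, so an excess that reflects extra testing could be read as extra onward transmission. The acknowledged limitations in 3.7 do not include this one.

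**Working it through.** **The plan's own figure.** The protocol gives no sample size for the secondary attack rate, but Table 2 shows that it already assumes detection rises with uptake. Take the cell for 15 contacts isolating and 60% uptake.

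- Control over two months: 2 index cases × 51 isolating. Mean 2 × 51 = 102, variance 2 × 51² = 5202.
- Intervention: index cases scaled by uptake, 2 × 60/30 = 4, each with 15 + 3 = 18 isolating. Mean 72, variance 4 × 18² = 1296.
- n = (1.960 + 0.842)² × (5202 + 1296) / (102 − 72)² = 56.7, so 57 per arm by the normal formula and 58 by a two-sample t-test. Table 2 states 58.

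All 17 Table 2 cells checked agree on this basis. (It uses the monthly index rate in Table 1. The text of 3.9 gives the intervention figure per week.)

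**Model for endpoint (v).** Let *c* be the share of in-school second-order contacts swabbed weekly, *s* the share of infections found by symptomatic testing, and *l* the share of the remainder found by weekly LFD in those swabbed.

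Detected share: D = s + (1 − s) × c × l

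- From 3.9 and Table 1: c = 0.3 in control; 0.4 to 0.6 under DCT.
- Assumed, not in the protocol: s = 0.3 to 0.5; l = 0.4 to 0.6.
- Also assumed: the true attack rate is equal in both arms, and consent to weekly testing is the consent that decides the route.

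In-school contacts only:

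| s | l | D, c = 0.3 | D, c = 0.4 | D, c = 0.6 | Ratio 40/30 | Ratio 60/30 |
|---|---|---|---|---|---|---|
| 0.3 | 0.4 | 0.384 | 0.412 | 0.468 | 1.07 | 1.22 |
| 0.3 | 0.6 | 0.426 | 0.468 | 0.552 | 1.10 | 1.30 |
| 0.5 | 0.4 | 0.560 | 0.580 | 0.620 | 1.04 | 1.11 |
| 0.5 | 0.6 | 0.590 | 0.620 | 0.680 | 1.05 | 1.15 |

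If half of the second-order contacts are household contacts with the same true rate, followed by routine data in both arms, the detected share becomes (D + s)/2:

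| s | l | c = 0.3 | c = 0.4 | c = 0.6 | Ratio 40/30 | Ratio 60/30 |
|---|---|---|---|---|---|---|
| 0.3 | 0.4 | 0.342 | 0.356 | 0.384 | 1.04 | 1.12 |
| 0.3 | 0.6 | 0.363 | 0.384 | 0.426 | 1.06 | 1.17 |
| 0.5 | 0.4 | 0.530 | 0.540 | 0.560 | 1.02 | 1.06 |
| 0.5 | 0.6 | 0.545 | 0.560 | 0.590 | 1.03 | 1.08 |

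With one route for everyone (l = 0 in this model) the ratio is 1.00.

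**Check on routine data used alone.** Take the limiting case in which every LFD-detected infection comes first and replaces a routine symptomatic test. Routine positives are then proportional to 1 − c × l.

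- 60% uptake: (1 − 0.6l)/(1 − 0.3l) = 0.76/0.88 = 0.86 at l = 0.4, and 0.64/0.82 = 0.78 at l = 0.6.
- 40% uptake: 0.84/0.88 = 0.95 and 0.76/0.82 = 0.93.

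This is an outer bound on a bias in the opposite direction.

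**The case against.** Several objections carry weight.

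- **Size.** The sensitivities are assumptions. At 40% uptake, which is within the protocol's range, the distortion is 10% or less. Household contacts dilute it further. A reader might infer that the between-arm contrast cannot be read at all. That goes too far: the bias has an expected direction, and uptake of weekly testing is itself recorded under 3.6 (vii).
- **Which consent.** The 30% and 40-60% figures are planning values for children's consent to weekly testing. Section 3.6 (v) speaks of consented participants in the study, and section 4 makes weekly testing and DCT separately voluntary. Equating the two is reasonable for a route that consists of weekly testing, but it remains an assumption.
- **School records.** A reader might infer that symptomatic positives among consenters are under-reported because they come through the school, and that this offsets the LFD effect. The protocol does not show it. Section 3.1 has positive cases report to the school, 3.2 requires schools to supply test results, and nothing indicates that reporting differs by arm.
- **Routine data as a cure.** A reader might infer that routine symptomatic positives alone would settle the comparison. Sections 3.1 and 4.1.2 have an LFD-positive person isolate and take a PCR swab for sequencing. The protocol does not say that this person also takes a routine symptomatic test. If some do not, routine positives fall most where weekly uptake is highest.
- **Already anticipated.** The authors see the source problem under co-primary (ii), and an analysis plan not available here might say how the routes are combined. But the ascertainment itself is fixed in Protocol 3.6 (v), and the rule on separate reporting is not stated there.

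These points limit the size of the concern and shape the remedy. They do not remove the unequal ascertainment.

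**Conclusion.** The concern holds for the pooled secondary attack rate as a between-arm contrast. If the stated uptake materialises and weekly LFD finds any infection that symptomatic testing misses, the detected rate among in-school second-order contacts will tend to be higher under DCT with no true difference.

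Under the assumed sensitivities, the spurious ratio is about 1.04-1.10 at 40% uptake and 1.11-1.30 at 60% for in-school contacts. It is about 1.02-1.06 and 1.06-1.17 if half of the contacts are household contacts. The protocol does not contain the figures needed to fix the size more closely. This is a secondary endpoint and the correction is cheap, so it should be made, but it does not threaten the co-primary analyses.

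**What to change.** In Protocol 3.6 (v):

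1. Query routine Test and Trace data for all in-school second-order contacts in both arms, whatever their consent.
2. Extend the like-for-like reporting rule of co-primary (ii) to (v). Give the between-arm rate separately by source: routine symptomatic PCR positives over all second-order contacts, and weekly-LFD positives over those actually tested.
3. Show household contacts separately.
4. State that the pooled rate is not the between-arm contrast.

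The cost is wording and a wider query. Routine data are already searched for non-consented contacts and for co-primary (ii), and schools already supply bubble membership under 3.7.

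There are two downsides. The routine-data rate omits asymptomatic infections. It may also be lowered where an LFD positive pre-empts a routine symptomatic test, which is more likely in the DCT arm. The two source-specific rates should therefore be read together.
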